#### Cognitive assessment and questionnaires

Some inconvenience and/or anxiety may occur due to time required to complete formal rating scales and questionnaires. The cognitive assessments impose some risk of emotional discomfort. Fatigue is associated with performing the cognitive tasks. The Geriatric

Depression Scale and the Geriatric Anxiety Inventory may warrant a follow-up if the subject receives a clinically significant score on any of these items (e.g., >5 on the GDS). These items will be scored immediately after completion by the subject.

#### ActiGraph physical activity monitor

Participants may experience red skin or discomfort from wearing the device around the waist/wrist too tightly or for an extended period of time.

#### PERSONNEL:

All staff and personnel associated with screening, collecting data, and analyzing data will have been trained in their laboratory and will have undergone all necessary research modules for safety and research ethics. [name] will meet with all staff on a regular basis to ensure that they are conducting research protocols appropriately.

Regarding use of the physical activity monitoring devices, participants will be guided through the use of the devices at T1 and will be reminded repeatedly throughout the study. We will help participants through the fitting process of the device and alert them to the sound the device will make when it is properly adjusted and ready to collect data. We will ensure that participants understand how the device works and how to correctly wear it to avoid any discomfort or incorrect usage. We will also instruct participants to notify us if any discomfort occurs. If any discomfort does arise as a result of wearing either of the physical activity monitoring devices, we will instruct participants to discontinue the use of the device.

**Cognitive assessments:** To alleviate any fatigue that may occur, participants are offered breaks during testing periods. They will also be provided with a referral for psychiatric consultation upon request or if their scores on the GDS and GAI are clinically significant, according to each evaluation's scoring guide. Any person scoring highly on the depression, anxiety, or cognitive impairment items will be referred back to their PCP for consultation.

### **10. End of Study**

There is the potential for direct benefit to participants randomized to the social motivation + self-transcendence health messaging arm of the study. Participants may experience direct benefits from participation such as improved cognition, mood, quality of life, physical fitness or decreased sedentary behaviour as a result of participating in the behavioural intervention over 3 months. There may be a reduction in central adiposity and cardiovascular benefits. In addition, we are hoping that participants will maintain reductions in sedentary behaviour beyond the completion of the study. The findings of this study provide information regarding the effect of simple and cost-effective behavioural intervention in reducing sedentary behaviour and improving brain health in a population at risk for cognitive decay. As such, the dissemination of this information stands to improve public health.

### **11. Transfer of Knowledge**

As part of the goals of this study, we intend to publish the results of these trials through scientific articles engaging in open science platforms, as well as through scientific conferences both locally and internationally. We believe that this intervention could be the first step

towards behavioural counselling with a precision medicine goal. This could potentially be a feasible way how to positively influence people's behaviour, especially patients at risk. Furthermore, positive results could potentially be translated into providing the active control group of this trial with the actual intervention. Moreover, if demonstrated that the intervention is successful in fulfilling its goals, we intend to offer it to a wider group of older adults, as we consider it a cheap, scalable, and effective way of motivating physical activity in sedentary older adults.

#### **List of Annexes:**

Annex A. Time Capsule.

Annex B. Study Partner cognitive battery and list of questionnaires.

Annex D. The Benefits of Physical Activity for Older Adults (informational material).

Annex F. Extrafamilial Study Partner Recruitment File.

Annex H. Extrafamilial study partner – script for partnering.

Cover Page

Statistical Design and Power

Study Title: The Healthy Aging Brain Study: A Remote Behavioral Intervention to Enhance Physical Activity in Older Adults.

Document creation date: March 7th, 2023

Statistical Design and Power

We will recruit 60 older adults over 60 years old (30 Intervention Group, 30 Control Group) from the PREVENT-AD cohort. This sample size was determined using power calculations that will allow us to identify a minimum detectable difference of 10.0%, with a common standard deviation of 14.0% (estimated from a similar physical activity intervention) with 80% power and a two-sided alpha of 0.05. Our research goal is to identify the neurobehavioral mechanisms underlying physical activity engagement in at-risk older adults and test the efficacy of a scalable, technology-based intergenerational behavior intervention on physical activity engagement. Our planned analyses and anticipated results for each Specific Aim are outlined below:

Aim 1) We will apply linear mixed effect models to determine the extent to which intergenerational social motivation enhances physical activity (primary outcome) and secondary outcomes (cognition, loneliness, self-efficacy, mood, and sleep) in at-risk older adults within the Intervention compared to the Control Group. Demographic variables (age, sex, socioeconomic status, neighborhood walkability) and AD multimodal risk score will be included as covariates of non-interest.

Aim 2) We will apply the NIH Science of Behavior Change theoretical framework to determine whether target mechanisms (social support, generativity or reward sensitivity) separately mediate the influence of the intervention on physical activity engagement. This approach will provide novel insights about target, potentially modifiable mechanisms that mediate successful behavior change in older adults at risk for AD.

Aim 3) To identify the individual differences and brain fingerprint that predict successful behavior change at the single subject level in older adults at risk for AD, we will analyze baseline behavioral and MRI data gathered during the intervention in addition to already acquired longitudinal multimodal brain and behavioral data. We will use both a-priori regions of interest (ROIs) vmPFC and salience network seed-based analyses of brain connectivity as well as data-driven whole brain multivariate pattern analyses per previous publications using data-driven approaches to predict clinical outcomes. We will apply rigorous machine-learning methods and independent linear regression models using leave-one-out cross validation (LOOCV) and bootstrap resampling to identify the brain networks that predict treatment response (physical activity engagement) at an individual level. We use methods that we published in a similar sample size of older adults. This approach will provide solid mechanistic insight into the brain basis of successful behavior change. We expect these results to be generalizable and yield single subject values.

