### 3. Method

#### 3.1 Recruitment

##### 3.1.1 Initial Contact

Older adult participants will be recruited through the PREVENT-AD cohort as an optional sub-study, by reaching out to potentially eligible participants by phone and email. Screening procedures will involve verbally screening potential participants over the phone. A staff member doing the screening will begin with an overview of the HABS project. The screener will then obtain verbal consent (see telephone script). The telephone script will ask questions concerning inclusion and exclusion criteria. The total time to administer all screening questions is approximately 40 minutes. The telephone screen will also assess the level of physical activity via self-reported physical activity. If eligibility is verified, a date and time will be scheduled for a virtual meeting between the participant and a researcher where the formal study consent will be signed. Those individuals that are deemed ineligible from the screening call will have their forms kept in a separate file on REDCap. This information will be used to quantify how many were ineligible from the screening call and the reasons for ineligibility.

The criteria will be assessed by one of the listed study personnel. No special expertise is required to evaluate screening responses. If a participant requires exclusion due to information received during a session, they will be contacted via telephone or email and informed that they have been excluded from further study, nevertheless remaining part of the PREVENT-AD cohort. The reason provided for their exclusion will be brief and will include a statement such as, "Based on the data collected in your last session, we will not require any further testing. As indicated in the beginning, participation depends on several factors and not all participants qualify for the entire study."

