Analyses on the resting state and task-based fMRI analyses are considered secondary. Briefly they will be modeled using the general linear model approach. First-level analyses will include all necessary nuisance regressors to minimize motion artifacts influence, spatial smoothing kernel and high pass filtering, as well as physiological aliasing for the low-frequency fluctuations in resting state data. To answer questions about the intervention effect and prediction of behavioural change, both a priori ROI seed-based analyses of functional connectivity are performed as well as data-driven whole-brain multi-voxel pattern analysis, modularity analyses and graph theory per several previous publications using data-driven approaches to predict clinical outcomes. Besides the primary outcomes, adherence and drop-outs are also included in the prediction model as outcome variables, to examine what individual characteristics affect participation in the current intervention. Robust-prediction models of MRI data and psychosocial measures will be generated using cross-validation methods to improve the generalization of the results.

Selection bias will also be considered in our study by comparing characteristics between the source population (i.e., PREVENT-AD participants) and the study sample. For eligible participants invited to participate in the study, we will document the proportion of those who decline and agree to participate. We will compare demographic information (age, sex, education, ethnicity, socioeconomic status, smoking status, and self-reported physical activity) between those who agree and those who refuse to participate using t-tests and chi-square tests of independence. Multivariate logistic regression models will be used to determine whether these characteristics are associated with acceptance relative to refusal to participate in the study.

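### The SAP attaches 80% power to the number recruited (60) with no allowance for lost accelerometer data; two losses per arm would leave about 75–76%

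*SAP*

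**What the plan says.** The SAP (Statistical Design and Power) gives a recruitment target: "We will recruit 60 older adults over 60 years old (30 Intervention Group, 30 Control Group". It ties its power statement to that number: "This sample size was determined using power calculations that will allow us to identify a minimum detectable difference of 10.0" percent, "with a common standard deviation of 14.0" percent, "with 80% power and a two-sided alpha of 0.05". It gives no attrition rate, no inflation factor and no separate number expected to be analysed. The protocol gives none either.

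The protocol does foresee loss of data:

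- Section 6b, on the prediction analyses: "adherence and drop-outs are also included in the prediction model as outcome variables".
- Section 9, on discomfort from a monitoring device: "we will instruct participants to discontinue the use of the device".
- Section 5.5 offers additional wear days to people who do not wear the devices consistently.

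Both primary outcomes in the section 6b table, steps per day and sedentary minutes per day, are accelerometer measures taken at baseline, week 2 and week 4. The protocol's own sample size (Executive Summary and section 4.1) is 120, not 60.

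**The concern.** Power depends on the number of people who contribute to the comparison, not on the number who consent. If 60 is the recruitment target and also the number used in the calculation, the stated power holds only if all 60 supply usable baseline and follow-up accelerometry. Someone with no follow-up week adds little or nothing to the group-by-time contrast.

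The power paragraph is the SAP's only guide to reading a null primary result. If power is overstated, a null result would be taken as stronger evidence against a 10-point difference than the data can give.

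**Working it through.** **Inputs.** Difference 10.0, common SD 14.0, two-sided alpha 0.05, power 80% and 30 recruited per arm (all SAP, Statistical Design and Power). Allocation is 1:1 (protocol section 4.2). Attrition is not given in either document, so 10–20% is an assumption used only to show a range.

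**Step 1: reproduce the SAP figure.** The standardised difference is 10/14 = 0.714.

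By the normal approximation, n per arm = 2 × (1.960 + 0.842)² × 14² / 10² = 30.8, which rounds up to 31. Power at n per arm is Φ(0.714 × √(n/2) − 1.960). At n = 30 this is Φ(2.766 − 1.960) = 79.0%.

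The two-sample t-test (noncentral t) needs 31.8, so 32 per arm, and gives 77.7% at 30.

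The normal approximation is the closer match to the stated 80%. By either method 30 per arm falls slightly short with complete data, so the 60 contains no hidden allowance for loss.

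**Step 2: remove participants.** The detectable difference by the normal approximation is (1.960 + 0.842) × 14 × √(2/n). The t-test value is solved numerically.

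| Analysed per arm | Power, normal | Power, t-test | Detectable with 80% power, normal | Detectable with 80% power, t-test |
|---|---|---|---|---|
| 30 (no loss) | 79.0% | 77.7% | 10.1 | 10.3 |
| 28 (two lost per arm) | 76.2% | 74.7% | 10.5 | 10.7 |
| 27 (10% loss) | 74.7% | 73.1% | 10.7 | 10.9 |
| 24 (20% loss) | 69.7% | 67.8% | 11.3 | 11.6 |

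**Step 3: separate the loss from the starting shortfall.** With two lost per arm, the gap from 80% is 80 − 76.2 = 3.8 points (normal) or 80 − 74.7 = 5.3 points (t-test). Of that, 1.0 or 2.3 points are already there at 30 per arm. The loss itself costs 79.0 − 76.2 = 2.8 points or 77.7 − 74.7 = 3.0 points.

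At 10% loss the gap from 80% is 5.3 (normal) or 6.9 (t-test) points. At 20% it is 10.3 or 12.2.

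**Step 4: the other sample size.** At the protocol's 120 (60 per arm) the same inputs give about 97% power by t-test with complete data, and about 93% at 48 per arm (20% loss).

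**The case against.** **The planned analysis is more efficient than a complete-case t-test.** Section 6b specifies a mixed model over three time points, which keeps people who supply only week 2, and the SAP adds covariates. If covariates explained 10% of the outcome variance (an assumed figure), the t-test power at 28 per arm would be 79.0%; at 15% it would be 81.2%. This stands as a reason to treat the figures above as approximate. It does not rescue the SAP's statement, whose sizing claims neither gain. Nor does a mixed model recover someone with no follow-up accelerometry.

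**The protocol works to limit loss.** It offers extra wear days (section 5.5), wear reminders in weeks 2 and 4 and next-day contact after a missed survey (section 5.3), and payment for completing accelerometry (sections 3.8.1 and 3.8.2). These make a low rate plausible. They do not make it zero, and they cannot recover withdrawals.

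**Some stronger readings are tempting, and the documents do not support them.**

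- A reader might infer that the two documents contradict each other, since one sizes for no loss and the other models drop-out. Section 6b names drop-out as an outcome but gives no count or rate, and the SAP is silent on loss. This is an omission, not a contradiction.
- A reader might say that two losses per arm always cost at least five points. That is true only of the t-test gap from 80%, and only because it includes the shortfall at 30 per arm. By the normal approximation, a five-point gap needs three losses per arm.
- A reader might treat every exit route in the protocol as attrition. The section 3.1.1 provision that people be "informed that they have been excluded from further study" sits in the screening text, and section 4.2 (Research Activities) places the anxiety, depression and cognitive screens before randomisation. Exclusions at that stage do not shrink the randomised arms. Section 5.5 describes two devices worn together, so stopping one need not remove both primary outcomes.
- A reader might conclude that the drop-out prediction model should be removed for want of events. That would rest wholly on an assumed rate, and it is not part of this point.

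**Conclusion.** The point holds as an unstated assumption with a modest, calculable effect. The SAP's 80% belongs to complete data on everyone recruited, and even then its inputs give 77.7–79.0%. Two losses per arm bring power to about 75–76%. An assumed 10–20% loss brings it to about 73–75% and then 68–70%, with a detectable difference of about 10.7–10.9 rising to 11.3–11.6.

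These figures rest on the SAP's difference and SD, equal loss in both arms, a simple two-group comparison, and an attrition range that the documents do not supply. They also rest on 60 being the intended number. If 120 is intended, the power concern largely disappears, although the SAP would still need to say how many participants it expects to analyse.

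**What to change.** First reconcile the 60 in the SAP with the 120 in the protocol's Executive Summary and section 4.1. Then, in the SAP power paragraph:

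1. State separately the number recruited and the number expected to supply baseline plus at least one valid follow-up accelerometer week. Use the sponsor's own attrition figure, or a stated range if it has none.
2. Restate power and the detectable difference for the second number, and name the method used.
3. If credit is taken for covariates or repeated measures, state the assumed variance explained or correlation.

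If 60 is kept and no better figure is available, the text could read: with 60 recruited and 10–20% assumed to lack usable follow-up accelerometry (54–48 analysed), power for a difference of 10.0% with SD 14.0% is about 73% falling to 68% by two-sample t-test, and the difference detectable with 80% power is 10.9–11.6%.

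The cost is one recalculation and a few sentences. No extra participants are needed. The downside is a less favourable stated power.

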## 2. Objectives and Hypothesis

This remotely administered multidisciplinary pilot proposal focuses on examining the efficacy of factors that have shown promise in motivating sedentary older adults to become more physically active as well as to investigate changes in patterns of activation of the neural networks, as indexed by MRI and fMRI, that support these factors and changes in physical activity. Brain imaging data has already been collected as part of the PREVENT-AD longitudinal cohort. We will not acquire any new brain or biomarker data but rather capitalize the dataset on these participants that already exist.

**Aim 1: To determine the efficacy of a novel motivational intervention to enhance physical activity in at-risk older adults.** In a four-week two-arm randomized controlled trial with cognitively normal older adults at-risk for AD, we hypothesize that social motivation combined with positively-framed health messaging + home-based physical training will increase physical activity compared to positively-framed health messaging + home-based physical training. We will examine the extent to which any differential physical activity engendered in the two groups is maintained at the longer-term crossover baseline period post-intervention or active control. In addition, we will test the extent to which participants

at higher risk of AD differentially benefit from the intervention and changes in physical activity. The primary outcome will be objectively-measured physical activity, secondary outcomes will be cognitive performance and functional brain connectivity, and tertiary outcomes will be fitness, mood and quality of life.

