### 4.2. Study design

The HABS study is a remote behavioural intervention that is conducted as a single-blinded randomized controlled trial. Recruited participants will be categorized as either high or low risk for Alzheimer's disease, in accordance with Aim 1 to determine the extent to which the behavioral intervention improves physical activity in at-risk older adults. Participant classification into high and low risk is based on their already known biomarker and cognitive status available from PREVENT-AD using a multimodal risk score. Note, that this does not involve collection of any new data and this data is not shared with participants as per the PREVENT-AD protocol. For participant classification into high risk, an individual's score is taken from a two-tier system of variables. The first tier involves variables where a positive result involves higher risk for Alzheimer's disease: Amyloid Tau Index (ATI)  $\leq 1$ , and p-tau in cerebrospinal fluid,  $\beta$ -Amyloid, and Total tau in PET, or APOE  $\epsilon 4/\epsilon 4$  or  $\epsilon 4/\epsilon 3$  status. A single positive value in any of these variables classifies the participant into the higher risk group. The second tier involves variables that independently are not sufficient for higher risk classification but together with a second variable might indicate higher risk: Overall cognitive performance (i.e., Repeatable Battery for the Assessment of Neuropsychological Status [RBANS]), episodic memory (i.e., Rey Auditory Verbal Learning Test [RAVLT]), hippocampal volume on MRI, APOE  $\epsilon 4/\epsilon 2$  status, Framingham Risk Score, and history of depression or consumption of psychotropic medication. Any combination of two variables from this tier classifies the participant into the higher risk group. Participants that are not classified into the higher risk group either because they had negative results to all risk variables or because they had a positive score to only one risk variable from the second tier, will be randomized into the low-risk group. We expect that approximately 50% of our participants will be in the high-risk group. We are using stratified randomization to ensure that each higher risk participant will be equally distributed across the intervention and control groups. The participants in each risk group are randomized to either a social motivation group (intervention) or control with a ratio of 1:1. The stratified randomization scheme is prepared by the Harvard Catalyst Biostatistical Group using a permuted block method with random blocks [16]. The randomization scheme will be uploaded in the REDCap randomization module. At the end of the first study period, participants will be offered to participate in a follow-up to ascertain maintenance which will consist of a cross-over into the alternative arm to which they initially were randomized. The study consists of two 4-week study periods with at least a 6-week washout period in between. This trial is registered on clinicaltrials.gov with an identifier NCT04315363. This study received ethical approval from Northeastern University Institutional Review Board (IRB).

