To test our main hypothesis that social motivation + self-transcendence messaging + home-based physical training will produce the largest increase in physical activity over the course of the 4-week intervention compared to the active control, we will perform repeated measures ANCOVAs (with group as a between-subject factor and pre-post session as a within-subject factor). This hypothesis will be examined by analyzing total number of steps and percent time sedentary. We will analyze structural/functional MRI connectivity to test the hypothesis that increased physical activity following the intervention is associated with enhanced brain connectivity between brain regions in reward valuation (i.e., ventral tegmental area and ventral striatum) and social processing (vmPFC). We will conduct seed-based functional connectivity analyses using methods as in our prior research [9, 29-31]. To mitigate the influence of motion, we will identify and address artifactual motion outliers in data modeling, and employ quality assurance software to mitigate head motion artifacts and physiological aliasing ([https://www.nitrc.org/projects/artifact\\_detect](https://www.nitrc.org/projects/artifact_detect)). We will control for the effects of demographic variables (e.g., age, sex, education, diet, mood, socioeconomic status, alcohol, vascular risk factors and sleep). We apply a whole-brain height threshold of  $p < 0.001$  ( $T = 3.24$ ) and false discovery rate cluster threshold of  $p < 0.05$ . We will examine brain modularity, which indexes the segregation between networks, and has previously been shown to predict cognitive gains after a physical exercise intervention [20]. In addition to these hypothesis-driven analyses, we will perform an agnostic, data driven multi-voxel pattern analysis of resting-state data using an approach published by our collaborator [21].

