After compiling all data across the 3 different data servers, data will be checked for completeness and correctness using frequency distributions (for missing data and out-of-range A-B values). Group differences at baseline are examined for variables including demographic factors (i.e., age, sex, educational level, socioeconomic status, culture), baseline sedentary time, self-report sitting time, and estimated fitness, in order to detect potential confounding factors. For the primary hypothesis that social motivation + self-transcendence messages decrease sedentary time more than an active control, all outcome measures about sedentary behaviour are first quantified using available software. Changes in sedentary behaviour (% daily sitting and lying time, minutes/per day in physical activity, count of steps) over time (3-time points) are analyzed using linear mixed effect models to account for the correlated data and likely heterogeneous variability.

Non-linear changes across 3-time points are also examined by including quadratic effects. These models will include a random intercept and slope to account for subject-specific changes as well as a group (2) x time (3) interaction fixed effect. This allows for modelling of the effect of our intervention as a function of both groups and time as well as accounting for potentially confounding covariates. All model assumptions will be tested both visually and formally and associations between covariates will be assessed to protect against multicollinearity.

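### The Aim 1 test of differential benefit by AD risk has no group-by-risk term in any planned analysis, and Aim 2 is moderation in the protocol but mediation in the SAP

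*SAP*

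**What the plan says.** **Aim 1, the promise.** Protocol section 2 commits the trial to testing how far participants "at higher risk of AD differentially benefit from the intervention and changes in physical activity". Section 4.2 links the high/low risk classification to Aim 1. It makes the classification "based on their already known biomarker and cognitive status available from PREVENT-AD using a multimodal risk score" and randomises 1:1 within risk group so that "each higher risk participant will be equally distributed across the intervention and control groups". On the split it says: "We expect that approximately 50% of our participants will be in the high-risk group".

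**Aim 1, the analysis.** Protocol 6b gives two models for the activity outcomes. One is a repeated-measures ANCOVA "with group as a between-subject factor and pre-post session as a within-subject factor". The other is a linear mixed model with random intercept and slope "as well as a group (2) x time (3) interaction fixed effect", with room for confounding covariates. SAP Aim 1 also uses linear mixed models and states: "Demographic variables (age, sex, socioeconomic status, neighborhood walkability) and AD multimodal risk score will be included as covariates of non-interest".

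**Aim 2.** The protocol hypothesises that adaptive decision-making (reward-effort computations, captured by the EEfRT), grit and growth mindset moderate the intervention's effect on change in activity. Under the same Aim number, the SAP asks whether social support, generativity or reward sensitivity each mediate that effect.

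**The concern.** A covariate entered as a main effect adjusts the group comparison. It does not show whether the group effect is larger in one risk group than in the other. That needs an interaction with group, or an equivalent contrast between strata, and none is written down although the randomisation was stratified with this aim in view.

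For Aim 2, moderation and mediation are different estimands. A moderator is a baseline characteristic across which the treatment effect varies. A mediator changes after randomisation and lies on the causal path. A mediation result does not answer the protocol's hypothesis.

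Following the SAP as written would leave the risk question with no estimate and the moderation hypothesis untested. If the analyses were added after the data are seen, the risk definition, the traits, the EEfRT measure and the time point would all be open to choice.

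**Working it through.** **1. Where a risk or trait interaction could appear**

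| Text | Terms stated | Group × risk? | Group × trait? |
|---|---|---|---|
| Protocol 6b, ANCOVA | group, session | no | no |
| Protocol 6b, mixed model | group × time, quadratic time, covariates | no | no |
| Protocol 6b, imaging and prediction models | imaging and psychosocial predictors, cross-validated | no | none stated |
| SAP Aim 1 | group effect, risk score as covariate | no | no |
| SAP Aim 2 | mediation, three named mechanisms | no | no |
| SAP Aim 3 | prediction of response, leave-one-out | no | none stated |

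The prediction models do not fill the gap. A trait that predicts change equally in both arms is a prognostic factor, not a moderator.

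**2. Aim 2 side by side**

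- Protocol: moderation by reward-effort computations (EEfRT), grit and growth mindset.
- SAP: mediation by social support, generativity and reward sensitivity.
- No variable is named in both. Reward sensitivity may overlap in concept with the EEfRT construct, but neither document equates them.

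**3. The SAP's own sample size, main effect only**

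Inputs from the SAP: difference 10, SD 14, two-sided alpha 0.05, power 80%.

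n per arm = 2 × (1.960 + 0.842)² × 14² / 10² = 30.8, so 31 per arm or 62 in total. At the stated 30 per arm, power is 79.0%. The SAP's 60 reproduces, and it covers the group comparison only.

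**4. Precision of a group × risk contrast**

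Assumptions: SD 14 applies to the change analysed (the SAP does not name the outcome), equal strata (Protocol 4.2), no dropout. Both sample sizes are shown because the SAP says 60 and the protocol says 120.

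SE = 14 × √(2/n_high + 2/n_low), with n per arm within stratum.

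- N = 60 (15 per cell): SE = 14 × √(4/15) = 7.23. The 95% CI half-width is 2.003 × 7.23 = 14.5. The difference detectable with 80% power (noncentral t, df 56) is 20.6, and power for 10 points is 27%.
- N = 120 (30 per cell): SE = 14 × √(4/30) = 5.11. The half-width is 1.981 × 5.11 = 10.1. The detectable difference is 14.4, and power for 10 points is 49%.

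The half-width for the group difference within one stratum, t × 14 × √(2/n), is 10.2 at N = 60 and 7.2 at N = 120.

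**5. Why the term must include time**

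Protocol 6b makes Week 0 one of the three time points. Suppose the true interaction is 0 at baseline and 10 points at Weeks 2 and 4. A two-way group × risk term averages over all three: (0 + 10 + 10)/3 = 6.7 points, two-thirds of the truth (balanced data, random intercept). With the random slope that 6b specifies, it recovered about 4 to 5 points under assumed variance components.

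**6. When the traits are measured**

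The Research Activities text in Protocol section 4 places the baseline neuropsychological and behavioural assessment after randomisation. Section 3.1.2 has the intervention arm invite a partner at the time of consent. The trait scores are therefore pre-intervention but post-allocation.

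**7. Multiplicity**

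Three traits on the two primary outcomes (steps and sedentary time) make 6 tests. If they are independent, the chance of at least one false positive is 1 − 0.95⁶ = 0.26.

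**The case against.** The strongest case against is weight. The protocol calls this a pilot. Neither question is among its three numbered hypotheses, and the wording of both Aims already implies effect modification, so what is missing is a model statement. With 60 participants the risk interaction would have an interval of ±14.5 points, wider than the 10-point difference the trial was sized on. This stands, and it is why the additions should be exploratory. It does not remove the gap: both are stated Aims, and low precision makes it more important to fix the contrast in advance.

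Three stronger readings are tempting and should not be drawn.

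- A reader might infer that entering risk as a main effect imposes an equal effect in both risk groups and so undermines the primary result. It does not. With 1:1 randomisation within strata, that model still validly estimates an average group effect.
- A reader might infer that the multimodal score must be removed because of collinearity, since the protocol says "associations between covariates will be assessed to protect against multicollinearity". That argument applies only if score and stratum are both entered. Section 4.2 describes a rule giving high or low risk and defines no continuous score, so the SAP's covariate may be the same classification.
- A reader might infer that the SAP supersedes the protocol on Aim 2, or that the SAP's mediators are not measured. Neither document says the first. The list of measures is in a spreadsheet outside these documents, so the second cannot be judged.

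**Conclusion.** The point holds and should be addressed before analysis. On the documents as written, the Aim 1 question of differential benefit by AD risk has no estimate, and the protocol's Aim 2 moderation hypothesis has no model in either document. The SAP puts a different question under the same Aim number. The comparison of text needs no numerical assumption. The primary group contrast is not affected.

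The precision figures describe what the remedy can deliver, not the size of the defect. They rest on the SAP's SD of 14% applying to the outcome analysed, equal strata and no dropout. On that basis the risk contrast will seldom be conclusive at either sample size.

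**What to change.** 1. **Aim 1.** Add an exploratory group × risk stratum × time term, with all lower-order terms, to the Protocol 6b mixed model, using the high/low stratum from randomisation. Report the difference between strata in the group contrast for change from baseline at Week 4 (and Week 2), and the group difference in change within each stratum, each with a 95% CI. Keep the SAP's covariate model for the primary contrast.

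2. **Aim 2.** Reconcile the documents so that both state the same question or questions.
   - If moderation is kept, fit group × trait × time terms (or group × trait on change from baseline) for one named EEfRT measure, grit and growth mindset. Label them exploratory and state the number of tests. Because the traits are assessed after allocation, compare trait scores between arms before interpreting them as baseline moderators.
   - If mediation is kept, report it as a separate question.
   - State that the prediction models do not test moderation unless a treatment-by-predictor term is added.

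**Cost.** A few model terms and reconciled wording. No new data are needed: risk status already exists from the cohort, and the EEfRT, grit and growth mindset are already scheduled (Protocol 5.5). The price is low precision and some added multiplicity, so these results can only be exploratory.
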